**16. Days return to work**

\_\_\_\_\_ days

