## **1. Introduction**

Mountain biking has developed into a popular sport performed by both amateurs and professionals. Physical activity is often related to an increasing risk of injury which may lead to high socioeconomic costs. To avoid accident-related injuries, each racing discipline demands its own set of specific skills and training regimens. The aim of this study is to perform a descriptive analysis of the causes and effects of mountain biking related injuries in amateur and professional athletes.

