## **3. Statistical analysis plan**

Data analyses will be performed using the Statistical Package for Social Sciences (SPSS), version 24.0 (IBM Corporation, Armonk, NY, USA).

Descriptive statistics [means  $\pm$  standard deviations (SD) and relative frequencies (%)] will be retrieved. Pearson correlations will be used to assess correlations between the outcome variables. Chi-squared tests will be applied to determine group differences of injury prevalence and the occurrence of severe, respectively mild injury events. Multivariate logistic regressions will be performed to evaluate predictive factors among the outcome variables (independent variables) of severe injury events (dependent variable; no severe injury = 0 versus severe injury = 1) in elites and amateurs separately. Independent samples t-tests will be used to evaluate mean group differences in demographics, and training and injury related variables between the elite and the amateur mountain bikers. P-values  $< 0.05$  will be considered as statistically significant. According to Cohen (1992), effect sizes will be calculated for the correlation analyses and defined as follows;  $r = 0.20$  small,  $r = 0.50$  medium,  $r = 0.80$  strong.

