**2. On what level do you participate in mountain biking?**

recreational       amateur       elite-amateur       professional

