**15. Days return to sports**

\_\_\_\_\_ days

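### Item 16 neither defines work nor records occupation, so an elite–amateur comparison of days to return to work is confounded by occupation to an unknown, possibly nil, extent

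*Combined protocol and SAP*

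**What the plan says.** The questionnaire has two time-loss items, each a single blank for a number of days: item 15, "Days return to sports", and item 16, "Days return to work". Item 16 does not say what counts as work and has no answer for a rider to whom it does not apply. No other item asks about occupation, employment or whether riding is the rider's job, and occupation is not among the domains that the Methods section says the questionnaire covers.

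The Introduction states the aim as a descriptive analysis of "mountain biking related injuries in amateur and professional athletes". Riding level comes from item 2, "On what level do you participate in mountain biking", which has four self-rated levels from recreational to professional. No rule says which levels form the elite group and which the amateur group.

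On the analysis, section 3 says: "Independent samples t-tests will be used to evaluate mean group differences in demographics, and training and injury related variables", comparing elite with amateur riders. It does not list the variables, and it gives no restriction or adjustment for these tests. A p-value below 0.05 "will be considered as statistically significant".

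**The concern.** The meaning of item 16 can change with the variable that defines the groups. For a rider whose work is riding, going back to work and going back to sport can be one event, so item 16 can repeat item 15. For a rider with another job, item 16 reflects the injury and also the physical demands of that job. Two groups with identical injuries could then differ on item 16. Nothing on the form would separate the part due to injury from the part due to occupation.

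The second problem concerns even the plain mean. A student or retired rider has no obvious answer. Some will leave the blank empty and some will write 0. That 0 cannot be told from the 0 of an employed rider who missed no day.

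At stake is the reading of the one item that bears directly on lost work. The Introduction gives as background that physical activity carries an "increasing risk of injury which may lead to high socioeconomic costs". Because occupation is not collected, neither problem can be repaired after the survey.

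**Working it through.** The documents give no sample size, standard deviation or expected value for item 16, so there is no figure to reproduce. The check has three steps. Every number in steps 2 and 3 is an assumption for illustration, except the 0.05 threshold, which is the SAP's.

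**1. Is item 16 in the planned tests?** A t-test needs a numeric variable. The numeric injury items are number of injuries (item 9), months since the latest injury (item 10), days to sport (item 15) and days to work (item 16). The SAP's class of injury related variables therefore includes item 16 on a natural reading, but this is an inference.

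**2. How large could the effect of occupation be?** Let both groups have the same injuries, with a mean of 30 days to return to sport. Let riders with another job return to work after a fraction *f* of their sport time, with the same *f* in both groups. Let riders who ride for a living return to work when they return to sport. Let *p* be the share of the elite group who ride for a living, and let no amateur do so. Then:

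- mean days to work, amateurs = 30*f*
- mean days to work, elites = 30*p* + 30*f*(1 − *p*)
- difference = 30 × (1 − *f*) × *p*

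For example, *f* = 0.25 and *p* = 0.5 give 30 × 0.75 × 0.5 = 11.25 days. A simulation with lognormal days (log-SD 1), a two-sided t-test at 0.05 and 4000 runs per setting gave these rejection rates:

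| *f* | *p* | Expected difference (days) | Rejected, 30 injured per group | Rejected, 100 injured per group |
|---|---|---|---|---|
| 0.25 | 0 | 0 | 4.0% | 4.2% |
| 0.25 | 0.25 | 5.6 | 21.6% | 71.3% |
| 0.25 | 0.5 | 11.3 | 62.5% | 98.6% |
| 0.25 | 1 | 22.5 | 96.9% | 100% |
| 0.5 | 0 | 0 | 3.8% | 5.0% |
| 0.5 | 0.25 | 3.8 | 7.6% | 20.3% |
| 0.5 | 0.5 | 7.5 | 20.5% | 56.8% |
| 0.5 | 1 | 15.0 | 55.4% | 96.0% |

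With *f* = 1 (other work and sport resumed together) the expected difference is 0 at every *p*, and rejection stayed between 3.4% and 5.0%. If other jobs kept riders away longer than sport did (*f* above 1), the formula changes sign. So even the direction is an assumption.

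**3. What do ambiguous zeros do to the mean?** Suppose employed amateurs lose 4 days on average and 20% of amateurs have no job.

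- All jobless riders leave the item blank: mean = 4.
- All write 0: mean = 0.8 × 4 = 3.2.
- Half write 0 and half leave it blank: mean = (0.8 × 4) / 0.9 = 3.6.

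The reported mean then depends on how riders without a job chose to fill in the blank, which the data cannot show.

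**The case against.** The strongest case on the other side has five parts.

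- **The gap can be real.** If a professional cannot ride for 30 days and riding is the job, 30 days of work were lost, and that is an effect of the injury. This stands. A reader might infer that the comparison measures type of job instead of injury. The documents do not support that: the days still reflect the injury, mixed with what the job demands.
- **Nobody need read severity from item 16.** Severity has its own item (12), and the SAP plans chi-squared tests and regressions on severe events. Injury type, recovery and return to sport are also recorded. This stands. A reader might infer that a longer work absence in elites would be taken as proof of graver injuries, but nothing in the plan uses item 16 in that way.
- **A 0 may be correct.** For mean work days lost per injured rider, someone without a job did lose none. This stands for that quantity. However, the plan does not say whether it wants that mean or the mean among working riders, and a mixture of zeros and blanks yields neither cleanly. Some riders may write a dash or a note in the blank, but nothing prompts them to.
- **The comparison is inferred and the sizes are assumed.** Both are true. The elite group may include elite-amateurs with other jobs, and ticking professional does not show that riding is the rider's only work.
- **Item 15 already gives a time-loss measure that is not tied to occupation.** True, so the time-loss comparison as a whole is not lost.

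What remains is that the share of elites who ride for a living decides whether the effect is nil or dominant, and the survey does not collect it.

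**Conclusion.** The point holds in a limited form. If item 16 is among the variables tested, the elite–amateur comparison is confounded by occupation, and its mean cannot distinguish riders without a job from employed riders who lost no day. Neither can be put right from the data collected.

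The size is unknown. On the assumed inputs in the table, the gap runs from 0 to 22.5 days, and it is 0 whenever no elite rides for a living or whenever other work and sport are resumed together. These results also assume that elites with other jobs and amateurs have jobs of similar demand.

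Severity is minor. This is one item of 25 in a descriptive survey that names no primary endpoint, a parallel item is available, and the documents do not show that a misleading difference will arise.

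**What to change.** **Questionnaire.** Add two ticks to item 16 in every language version: *no paid work at that time* and *riding is my work*.

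**SAP.** Add text to this effect:

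- Riders with no paid work at the time of injury are left out of the mean of item 16, and their number is reported.
- Item 16 is presented separately for riders whose work is riding and for riders with other paid work. The professionals' work loss is thus still reported.
- Any elite–amateur test of item 16 is made within riders with other paid work.
- Item 15 is the main time-loss comparison between the groups.

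**Cost.** The form changes slightly in each of the five languages, and the SAP gains a few sentences. The work-loss test will include fewer elite riders and so have less power.

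**Limits.** The ticks do not remove differences in job demands among riders with other work, so that test still needs cautious wording. They also do not settle which item 2 levels make up the elite group, and the SAP should state that separately.

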**17. Did you fully recover from the injury?**

full recovery     partial recovery

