## **2. Methods**

A survey (as outlined below) of mountain biking related injuries will be conducted on the participants of the Swiss Epic mountain bike event in 2017 held in Valais. The retrospective questionnaire is designed in accordance with existing literature ((Gaulrapp et al., 2001; Lareau and McGinnis, 2011), will include 25 questions and will be translated into English, French, Italian, Spanish and German. The participants will be asked to tick the most appropriate answer. The questionnaire aims to assess the athletes' 1) basic demographics, riding level and years of experience, 2) number of races per year and mean hours of training per week, 3) number and kind of suffered injuries related to mountain biking and medical treatment requirement, 4) and amount and kind of protective gear items.

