**9. Number of injuries obtained during mountain biking**

\_\_\_\_\_

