**10. How long ago was your most recent injury?**

\_\_\_\_\_ /months

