**11. Mechanism of injury**

loss of control       loss of traction       collision with object       collision with rider       mechanical problem  
 unknown       other \_\_\_\_\_

**12. Severity of injury** (if more than one injury occurred, choose the most severe one)

no medical treatment needed     self-administered medical treatment     MD administrated medical treatment     Medical treatment in ER     Overnight hospitalization

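### Recovery is asked once, at no set time after injury and with no answer for riders still healing, so unfinished healing cannot be told from lasting deficit, and time since the rated injury may be unknown

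*Combined protocol and SAP*

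**What the plan says.** The Methods section describes a single survey of participants in the 2017 event. It calls the instrument retrospective ("The retrospective questionnaire is designed in accordance with existing literature") and mentions no repeat assessment.

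The relevant questionnaire items are:

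- Item 9, "Number of injuries obtained during mountain biking", takes a free number and sets no look-back window.
- Item 10, "How long ago was your most recent injury", is answered in months.
- Item 12 (severity) instructs the rider: "if more than one injury occurred, choose the most severe one".
- Items 13 to 17 carry no instruction of their own about which injury is meant.
- Items 15 and 16 (the latter is "Days return to work") each take a number of days and offer no answer for a rider who has not yet returned.
- Item 17, "Did you fully recover from the injury", has two answers, full or partial, and no reference time.

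The SAP section plans t-tests for "mean group differences in demographics, and training and injury related variables between the elite and the amateur mountain bikers" and chi-squared tests for "group differences of injury prevalence and the occurrence of severe, respectively mild injury events". It does not name recovery and does not mention time since injury.

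**The concern.** The Introduction gives the aim as describing the causes and effects of injuries, and items 15 to 17 are the main measures of effect. Recovery status means little without knowing how long after the injury it was recorded. One rider may be answering about an injury a few weeks old and another about one many years old. If both tick partial recovery, the data cannot show which of them has a lasting problem.

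Two results are at stake. One is the descriptive share recovered, which depends partly on the age of the injuries reported. The other is any elite-amateur comparison of recovery made under the SAP's broad wording on injury-related variables. If the two groups differ in how recent their rated injuries are, they will differ in reported recovery even when healing is identical.

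**Working it through.** **Reading the items together.** For a rider with one injury, items 10, 12 and 17 all refer to it, so time since injury is available, although the SAP does not use it. For a rider with k injuries, item 10 dates the latest and item 12 rates the worst. If severity is unrelated to order (an assumption), the two coincide with probability 1/k: 50% for k = 2, 33% for k = 3, 20% for k = 5. If items 13 to 17 follow item 12, adjusting by item 10 would often use the wrong date.

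**Size.** The documents give no sample size, recovery rate or time-since-injury figure, so there is nothing to reproduce. What follows is an illustration on assumed inputs.

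- Healing time is exponential with the same median in both groups: 1, 3 or 6 months. Every injury eventually heals fully.
- Time since the rated injury is exponential with mean m.
- Mean healing time is h = median / ln 2, that is 1.443, 4.328 or 8.656 months.
- The share still healing when asked is h / (h + m). All of these are taken to tick partial recovery.

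Example, median 3 months: m = 12 gives 4.328 / 16.328 = 26.5%; m = 24 gives 4.328 / 28.328 = 15.3%; the gap is 11.2 points.

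| Mean months since injury, group A vs B | Median healing 1 month | 3 months | 6 months |
|---|---|---|---|
| 12 vs 12 | 10.7% vs 10.7%, gap 0 | 26.5% vs 26.5%, gap 0 | 41.9% vs 41.9%, gap 0 |
| 12 vs 24 | 10.7% vs 5.7%, gap 5.1 | 26.5% vs 15.3%, gap 11.2 | 41.9% vs 26.5%, gap 15.4 |
| 6 vs 18 | 19.4% vs 7.4%, gap 12.0 | 41.9% vs 19.4%, gap 22.5 | 59.1% vs 32.5%, gap 26.6 |

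Gaps are in percentage points, from unrounded shares. Every gap is false, because healing is the same in both groups. The first row shows that the descriptive share is affected even without a group difference: 11% to 42% are labelled partial although nobody has a lasting deficit.

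If a share L of injuries truly leaves a deficit in both groups, the partial share is L + (1 − L) × h / (h + m), so each gap shrinks by the factor 1 − L. With L = 10%, 22.5 becomes 0.9 × 22.5 = 20.3 points.

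**Would restricting to injuries at least 12 months old help?** The share of injuries kept is exp(−12 / m): exp(−2) = 13.5% for m = 6 and exp(−0.667) = 51.3% for m = 18. The share still healing among those kept is exp(−12 / h) × h / (h + m). With a median of 3 months this is 0.0625 × 0.419 = 2.6% against 0.0625 × 0.194 = 1.2%, a gap of 1.4 points. With a median of 6 months it is 0.25 × 0.591 = 14.8% against 0.25 × 0.325 = 8.1%, a gap of 6.7 points. Restriction removes most of the false gap but discards most of one group's data.

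**The case against.** The case on the other side is substantial, and much of it stands.

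- *Partial recovery is not defined as permanent.* A reader might infer that the plan counts healing injuries as lasting deficits. Nothing in the documents says so. What holds is that the two cannot be distinguished.
- *No recovery comparison is named.* The chi-squared tests are for prevalence and severity, and the t-tests are for means, whereas item 17 is binary. Recovery could enter only through the general phrase on injury-related variables. The planned correlations between outcome variables could include item 10, but that would not condition recovery on it.
- *The direction is not determined.* A reader might infer that the more often injured group must look slower to recover, because its injuries are more recent. That is true of the most recent injury. If items 13 to 17 describe the most severe one, it does not follow: with a constant injury rate and severity unrelated to order, the worst injury falls uniformly over the riding career however many there were, and a longer career makes it older on average.
- *Respondents are racing.* Riders too injured to start are absent, which limits the share still healing. If, as an assumption, half of those still healing do not start, the 6 against 18 month case at median 3 becomes 0.2095 / (0.2095 + 0.581) = 26.5% against 0.097 / (0.097 + 0.806) = 10.7%. The gap falls from 22.5 to 15.8 points: smaller, but not gone. For the same reason, unfinished durations in item 15 are probably few. Item 16 is affected only for riders who race while still off work. The documents do not support a claim of material shortening in days to return.

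None of this supplies the missing answer option, the date of the rated injury, or an analysis by time since injury.

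**Conclusion.** The point holds as a limit on what items 15 to 17 can show, chiefly item 17. Even if the plan is followed exactly, healing and lasting deficit are merged, and for riders with several injuries the age of the rated injury may be unknown. The recovered share depends partly on injury age, and an elite-amateur comparison of recovery may be biased if the groups differ in recency.

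Size rests entirely on the assumed exponential healing and recency: from 0 at equal recency, through 5 to 15 points at 12 against 24 months, to 12 to 27 points at 6 against 18 months. The upper values need a threefold difference in mean recency, and no figure in the documents shows that elites and amateurs differ at all. The change is worth making because it is cheap and the missing answers cannot be reconstructed after the survey.

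**What to change.** 1. **Answers.** Add a still-recovering answer to item 17 and a not-yet-returned tick to items 15 and 16. The tick will probably be used by few riders, mainly at item 16.
2. **One injury, one date.** State that items 10 to 17 all describe the same injury, the most severe, and ask months since that injury. If the date of the latest injury is still wanted, keep it as a separate line.
3. **SAP.** Report item 17 as recovery status at survey, by time since injury. Stratify or adjust any elite-amateur comparison of recovery for time since injury, using a chi-squared test within strata or a logistic model, since the outcome is binary. This is preferable to discarding injuries under 12 months: the documents give no basis for that cutoff, and in the illustration it keeps only about 14% of one group's injuries.

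If the data are already collected, stratify by item 10 among riders reporting one injury at item 9, and label the result recovery status at survey.

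Cost: small wording changes in five language versions, a short SAP addition, and fewer riders per stratum. Limiting a completed survey to single-injury riders also narrows the population described.

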**18. Do you experience injury related pain before/during/after mountain biking?**

before     during     after     no

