## Mountain biking Injury Questionnaire

*Thank you for agreeing to take part in this important questionnaire about mountain biking injuries. The information we can obtain from this survey may help to improve the knowledge about injury prevalence in mountain biking. With this knowledge, it may be possible to improve safety in future and prevent injury.*

*Be assured that all answers you provide will be kept in the strictest confidentiality. This survey is anonymous. Do not write your name on the survey.*

*Please tick only the most correct answer.*

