**19. Do you experience NOT injury related pain before/during/after mountain biking?**

before     during     after     no

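### Item 18 does not say that the injury must come from mountain biking, so its count of lasting pain may include pain from other injuries

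*Combined protocol and SAP*

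**What the plan says.** The aim in Section 1 (Introduction) is a "descriptive analysis of the causes and effects of mountain biking related injuries". Section 2 (Methods) lists among the topics of the questionnaire the "number and kind of suffered injuries related to mountain biking and medical treatment requirement"; pain is not among the four topics listed there.

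On the form, item 9 opens the injury block and states the origin: "Number of injuries obtained during mountain biking". Items 10 to 17 then ask about timing, mechanism, severity, location, type, days lost and recovery. Item 17 ends the block with "Did you fully recover from the injury". Item 18 follows: "Do you experience injury related pain before/during/after mountain biking". Item 19 is its counterpart: "Do you experience NOT injury related pain before/during/after mountain biking". Both offer the boxes before, during, after and no. Neither has a skip rule or a not-applicable box.

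Section 3 (Statistical analysis plan) does not name item 18 or pain. The nearest text is the comparison of "training and injury related variables between the elite and the amateur mountain bikers".

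**The concern.** Item 18 is the only question on continuing pain from injury, and such pain is one effect of injury within the stated aim. Its wording leaves the source of the injury open. A rider with pain from an old skiing or work injury finds no other place for it, since item 19 excludes pain due to injury. Such a rider may tick item 18, and so may a rider who answered zero to item 9.

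If that happens, the reported percentage mixes two sources. Riders may also read the item differently, some narrowly and some broadly, so that it measures different things in different people. If pain from other injuries is more common among elites or among amateurs, a difference between the groups on this item could partly reflect that. The data could not be sorted out afterwards: the survey is anonymous, and no item asks for the source of the pain.

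**Working it through.** The documents give no expected prevalence of pain, so there is no planned figure to reproduce. The check is a comparison of wording, followed by an illustration on assumed values.

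**Wording**

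| Item | Origin of the injury | Link to the injury already described |
|---|---|---|
| 9 | stated: mountain biking | opens the block |
| 17 | not repeated | yes, refers to *the* injury |
| 18 | not stated | none |
| 19 | excludes all injury-related pain | none |

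1. In item 18 mountain biking is attached to before, during and after. It is a time reference, not a source.
2. Items 18 and 19 together divide pain into two classes, due to injury and not due to injury. Pain from an injury outside mountain biking is, literally, in the first class.
3. A rider with zero in item 9 can tick a pain box in item 18. Item 9 can identify these riders at analysis.
4. A rider with at least one injury in item 9 may have pain from either source or both. No item separates them, so restricting the analysis by item 9 does not solve this part.

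**Illustration (all three inputs are assumptions)**

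Let *p* be the share of riders with pain from a mountain biking injury, *o* the share with pain from another injury, independent of the first, and *s* the share of those with other-injury pain who would tick item 18 because of it. Then

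reported share = 1 − (1 − *p*)(1 − *s·o*).

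With *p* = 0.20:

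| *o* | *s* = 0 (read in context) | *s* = 1 (read literally by all) |
|---|---|---|
| 0.05 | 1 − 0.80 × 1 = 0.20 | 1 − 0.80 × 0.95 = 0.24 |
| 0.10 | 0.20 | 1 − 0.80 × 0.90 = 0.28 |
| 0.15 | 0.20 | 1 − 0.80 × 0.85 = 0.32 |

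For these inputs the overstatement runs from 0 to 12 percentage points (0.32 − 0.20). If *p* is 0.20 in both groups, *s* = 1, and *o* is 0.05 in elites and 0.15 in amateurs, the item shows 24% against 32%, an 8-point difference with no true difference behind it. That gap comes entirely from assuming unequal rates; with equal *o* and *s* in the two groups it is zero.

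**The case against.** The strongest defence is context. The form's title is about mountain biking injury, and riders are told that it is "this important questionnaire about mountain biking injuries". Item 9 sets the scope once, and items 10 to 17 rely on it without repeating it; taken strictly, the same literal reading would open mechanism and severity to other injuries too. Item 18 comes directly after a question about *the* injury. A rider who carries that frame forward can properly answer no to item 18 despite pain from another source.

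Much of this stands. A reader might infer that riders with other-injury pain are obliged to tick item 18, or that the percentage is certainly too high. The documents support neither, because how riders will read the item is unknown. What the defence does not remove is the change at items 18 and 19: the link to *the* injury is dropped, and item 19 leaves the injury frame to ask about all other pain. Read as a pair, the two items invite the broad reading.

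A second defence is that the plan specifies no analysis of item 18. The sentence on injury-related variables concerns t-tests of means, and item 18 is a set of tick-boxes; the chi-squared tests are for injury prevalence and for severe and mild events. This too is correct. An elite-amateur comparison of item 18 is a possible use under the stated aim, not a written one.

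**Conclusion.** The point holds as an ambiguity of wording. Item 18 leaves the origin of the injury open, item 19 gives pain from other injuries no alternative place, and nothing ties the answer to item 9. The percentage with lasting pain from mountain biking injury may be overstated, by an amount that the documents do not allow one to estimate and that may be zero. The range of 20% to 32% above shows only how the size depends on two unknowns: how common other-injury pain is, and how many such riders read the item literally.

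Two stronger readings should be avoided. A reader might infer that the plan counts pain from any injury as an effect of mountain biking; Section 3 contains no rule attributing item 18 to anything. A reader might also infer that the study's account of injury effects depends largely on this item. It does not: item 12 records the treatment needed, up to a hospital stay, and supplies the severe-injury outcome of the regressions if severity is taken from it; items 15 to 17 record days lost and recovery. No stated figure in the plan is affected. The reasons to act are that the remedy is nearly free and that the sources cannot be separated once the anonymous forms are in.

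**What to change.** Before distribution:

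- Reword item 18 to ask about pain from an injury obtained in mountain biking, using item 9's description of the origin. Keep the question about timing and the existing boxes (before, during, after, no).
- Add a box for pain from another injury only, and a box for not applicable because the rider has had no mountain biking injury.
- Leave item 19 for pain not due to any injury.
- Add one sentence to Section 3: item 18 is reported as an effect of mountain biking injury only among riders whose item 9 answer is at least 1. In that group, the box for another injury only counts as no pain from mountain biking injury.

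The sentence in Section 3 needs no change to the form, but alone it removes only riders without a mountain biking injury. The rewording is what separates the sources in the others.

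The cost is one slightly longer item with two more boxes, translated in the five language versions, and one sentence in the plan.
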